Verification of each PSAP was performed with the Audioscan Verifit 2 Speechmap system using an on-ear probe microphone to measure output. The International Speech Test Signal (ISTS) was used to obtain real-ear unaided responses (REUR) for 50 dB SPL input, followed by aided responses at 50 dB SPL and 65 dB SPL. The output of each device was adjusted so that the long-term average speech spectrum of the ISTS would approximate National Acoustic Laboratories Non-Linear 2 (NAL-NL2) targets within +/- 5 dB SPL where possible. For devices with limited fine-tuning ability, targets in the 1 kHz – 2 kHz range were given preference. To confirm loudness comfort, swept tones were presented from 0.25 – 8 kHz at 85 dB SPL, followed by pink noise at 80 dB SPL. Participants rated the above stimuli on a 7-point loudness scale (7 = uncomfortably loud). If participants rated either loudness test as a 7, gain was reduced and the loudness test was repeated until a comfortable loudness level was reached. In cases where gain was reduced following the loudness comfort test, aided responses to ISTS were re-measured with the final device settings to be used in the speech perception task.

In the speech perception task, subjects were played a series of sentences and instructed to repeat them back verbatim. The sentences were all taken from the same corpus, developed by Helfer, Merchant, and Freyman (2016). Sentences in this corpus all have the same syntactic structure: *Name found the color noun and the adjective noun here* (with the five underlined words denoting the target words which varied across sentences). A sample sentence is *Theo found the pink menu and the true item here*. All sentences were recorded from a female speaker. The subjects performed the task once while using a PSAP (aided) and once without (unaided), with different sets of sentences. Half of the

participants in each device group began with the unaided test block, and half with the aided; this factor was randomized within each device group. Their responses were audio-recorded and analyzed and scored off-line.

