Subjects performed the task in a sound booth with three loudspeakers. Target sentences were played from a loudspeaker located directly in front of the participant and maskers were played from loudspeakers located 60 degrees to the right and left. Maskers were either speech-shaped steady-state noise (SSN), speech-shaped envelope-modulated noise (SEM), or sentences from the same corpus as the stimuli, also spoken by other female talkers. Masking sentences began at a random point in the sentence, with the beginning of the sentence appended to the end, in order to assist participants in segregating the target sentence (which always began with Theo, Victor, or Michael) from the masking sentences. Target presentation level and signal-to-noise ratio (SNR) were both varied as well: target sentences were presented at either 50 decibels A or 65 decibels A, and maskers were presented at levels corresponding to 0 decibels SNR and -6 decibels SNR.

Nine sentences (45 target scoring words) occurred in each of twelve auditory conditions (3 masker types by 2 presentation levels by 2 SNRs), all randomized within each block (aided vs. unaided), making 216 sentences across 24 total conditions. In addition, before each block, subjects were given 12 practice trials (four with each masker type) to become accustomed to doing the task with or without the device. Subjects were scored on the speech perception task in terms of percentage of correct target words accurately repeated in each condition.

At the end of each of the two blocks, subjects were asked to indicate how much effort they needed to expend to complete the task on a scale of 1 (very little effort) to 10 (a great deal of effort).

Participants also completed a brief survey after the speech perception task. This survey asked them to indicate the extent to which participants thought the device would be helpful in the real world; how willing they would be to use the device in the real world; whether they would recommend the device to others; and how comfortable they found wearing the device.

Statistical Analysis Plan

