Dependent variables to be analyzed are performance on the speech perception task, benefit of use of the device, and self-rated listening effort. Performance will be measured as percent of target words accurately repeated; benefit will be measured as percent correct with device minus percent correct without device. Listening effort will be measured on ten-point scale (10 being the greatest effort, 1 the least).

Between-subjects variables to be measured are device (i.e., which of the four devices the participant used), age, and hearing loss (better-ear Pure Tone Average). Within-subject independent variables to be analyzed are device condition (i.e., with vs. without device) and acoustic properties of the stimuli: presentation level of target sentences (soft vs. loud), type of masking noise (SEM noise, SSN noise, or competing speech maskers), and signal-to-noise ratio (-6 dB or 0 dB).

Statistical analysis will be done with separate Repeated Measures ANOVAs for Performance, Benefit, and Self-Rated Effort. Responses to the post-experiment questionnaire will be analyzed qualitatively.

References

<https://doi.org/10.1001/jamaoto.2019.0667>.

Nasreddine, Z. S., Phillips, N.A., Bédirian, V., Charbonneau, S., Whitehead, V., Collin, I., Cummings, J. L. & Chertkow, H. (2005). The Montreal Cognitive Assessment, MoCA: A brief screening tool for Mild Cognitive Impairment. *Journal of the American Geriatrics Society*, 53, 695-699. <https://doi.org/10.1111/j.1532-5415.2005.53221.x>.

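### Block order is randomised within each device group but left out of the analysis, so a constant block effect inflates the error term and costs power

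*Combined protocol and SAP*

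**What the plan says.** The section on study methods and procedures describes a two-block within-participant comparison: "The subjects performed the task once while using a PSAP (aided) and once without (unaided), with different sets of sentences". Order is a controlled design factor: one half of "participants in each device group began with the unaided test block, and half with the aided; this factor was randomized within each device group". It adds that "before each block, subjects were given 12 practice trials (four with each masker type) to become accustomed to doing the task", in either device condition. Effort is rated once, at the end of each block.

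The Statistical Analysis Plan then lists its variables. For the first group it states: "Between-subjects variables to be measured are device (i.e., which of the four devices the participant used), age, and hearing loss". For the second group it states: "Within-subject independent variables to be analyzed are device condition (i.e., with vs. without device) and acoustic properties of the stimuli", the latter being presentation level, masker type and signal-to-noise ratio. Benefit is a difference score: "benefit will be measured as percent correct with device minus percent correct without device". The method is given in one sentence: "Statistical analysis will be done with separate Repeated Measures ANOVAs for Performance, Benefit, and Self-Rated Effort". Neither block order nor block position is named in these lists or elsewhere in the plan.

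**The concern.** The trial balances and randomises a factor by design and then ignores it in the analysis. A block effect is plausible: each block has 108 scored sentences built on one template, so participants may improve with exposure or tire. Practice trials and different sentence sets may shrink such an effect, but they do not rule it out. The effort rating is exposed to fatigue because there is only one rating per block.

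If a block effect exists and is not modelled, it enters the residual of every test built on aided minus unaided:

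- aided versus unaided on Performance;
- its interaction with device;
- the device comparison of Benefit;
- the aided-unaided contrast on Effort.

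These tests carry the study's stated objectives. The risk is a missed benefit or a missed difference between devices, not a false claim. A block effect that is the same in all acoustic conditions does not touch the masker, level and signal-to-noise effects (on Performance or Benefit), nor the main effect of device on Performance.

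**Working it through.** **Inputs from the documents.** Four device groups; one aided and one unaided block per participant; order split half and half within each device group; 9 sentences × 12 conditions = 108 scored sentences per block, and 108 × 2 = 216 in all, which matches the stated total.

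**Inputs assumed.** The documents give no sample size, alpha, SD of individual benefit or block effect, so there is no power figure to reproduce. Assumed here: two-sided 5% tests; SD of a participant's aided-minus-unaided difference of 6, 8 or 10 percentage points (1.5 scale points for effort); d of 1, 2, 3 or 5 points (0.25, 0.5 or 1 for effort); 80% power when order is in the model; 10 participants per device for simulations.

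**Model.** A participant's benefit is: true benefit + device effect + s·d + error. Here s = +1 if the unaided block came first and −1 if the aided block came first.

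1. *Bias.* With half of each group at s = +1 and half at −1, s·d averages to zero in every device mean. The true variance of the mean benefit stays SD²/N. Simulation confirms this: at SD 8 and d = 5, the empirical SD of the mean times √N is 8.01.
2. *Estimated error.* Without an order term, the residual mean square estimates SD² + d²·N/(N − 4), or about SD² + d² in large samples.
3. *Consequence.* The test statistic is divided by an inflated standard error. In large samples, with 1.96 + 0.8416 = 2.8016 as the standardised effect giving 80% power:
   - power = Φ(2.8016 − 1.96·√(1 + d²/SD²))
   - actual type I error = 2·Φ(−1.96·√(1 + d²/SD²))

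Worked example, SD 8 and d = 5: variance ratio 89/64 = 1.391; its root is 1.179; 1.96 × 1.179 = 2.311; power = Φ(0.490) = 68.8%; type I error = 2·Φ(−2.311) = 2.1%.

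**Power of the aided-unaided test without order (80% with order):**

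| d (points) | SD 6 | SD 8 | SD 10 |
|---|---|---|---|
| 1 | 79.2% | 79.6% | 79.7% |
| 2 | 76.9% | 78.3% | 78.9% |
| 3 | 72.9% | 76.1% | 77.5% |
| 5 | 59.9% | 68.8% | 72.9% |

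Actual type I error of the nominal 5% test at SD 8: 4.8% (d = 1), 3.6% (d = 3), 2.1% (d = 5).

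Effort, SD 1.5: d = 0.25, 0.5 and 1 scale point give 79.2%, 76.9% and 67.2%.

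**Simulation** (40,000 runs, 4 × 10 participants, 5/5 order split, SD 8, d = 5):

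| Test | Power, no order | Power, with order | Null rejection, no order | Null rejection, with order |
|---|---|---|---|---|
| Aided vs unaided | 0.678 | 0.801 | 0.020 | 0.051 |
| Device comparison of benefit (3-df F) | 0.603 | 0.796 | 0.012 | 0.048 |

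The device F test without order gives 0.795, 0.774 and 0.730 at d = 1, 2 and 3.

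**Second simulation, with d in units of SD** (20,000 runs, 10 per device, no order term). The error variance is multiplied by 1.07 at d = 0.25 SD and by 1.28 at d = 0.5 SD. Type I errors (aided-unaided, device benefit) are 0.041 and 0.038 in the first case, and 0.027 and 0.020 in the second. Null rejection at 6 and 20 per device is similar. With order in the model, all return to about 0.05.

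**The case against.** The strongest reply is that the design has already dealt with the serious hazard. Counterbalancing within device removes bias from a constant block effect and pushes type I error below nominal, so no false claim of benefit can follow. What remains is lost power, and its size is wholly assumed. At d = 1 the loss on the aided-unaided test is 0.3 to 0.8 percentage points and at d = 2 it is 1.1 to 3.1. Nothing in the documents shows that d reaches 3, and the practice trials and separate sentence sets point to a smaller value. All of that stands. It limits the weight of the point but does not remove it, since the correction costs almost nothing.

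Two limits of scope also stand. First, the tests are conservative only for a constant, additive effect under the stated equal split. Under simple, unbalanced randomisation the simulated type I error is about 5%, with only a power loss. Second, carryover that differs by order is a separate problem. It biases the aided-unaided contrast, and an order term does not remove it. With 10 per device, d = 0.5 SD and a carryover of 0.5 SD, null rejection was 0.17 without the order term and 0.33 with it.

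Finally, the plan is brief: it gives no model equation, interactions or error terms. The exact model is therefore partly a reconstruction, but the variable lists are complete sentences and order is not in them.

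**Conclusion.** The concern holds. The analysis as written omits a factor that the trial itself balances and randomises, and a constant block effect would go into the error term of the tests that address the main objectives. The estimates are not biased under the stated equal split. The documents report no unequal split; if the analysed groups were unequal, the aided-unaided effect would also shift by d × (n1 − n2)/(n1 + n2), where n1 and n2 are the numbers starting unaided and aided.

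The loss is negligible for a block effect of 1 point and material from about 3 points, with the device comparison of benefit losing most. The SD, block effect, sample size and alpha are all assumptions, so confidence in the practical size is medium. This is a change that should be made, not one on which the validity of the trial turns.

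**What to change.** Add block order (aided first or unaided first) as a between-subjects factor in all three ANOVAs:

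- **Benefit:** enter order as a main effect, without order by device.
- **Performance and Effort:** enter order and its interaction with device condition, which is equivalent to block position. Leave out order by device by condition.
- **Reporting:** give the aided-unaided effect averaged equally over the two orders.

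Leaving out the device-specific order terms assumes that the block effect is similar across devices; the plan should say so.

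The cost is one sentence in the plan and about one error degree of freedom for the affected tests, with no new data. In the simulations with no block effect, adding order changed power by no more than simulation error. The methods are written in the past tense, so data collection appears complete. The addition should therefore be dated and declared as a change made after collection, justified by order being a randomised design factor.

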Aging and Speech Perception in Complex Listening Environments
NCT03704142

2/28/2022

Study objectives

The goal of this study was to assess the effectiveness of, and benefits provided by, several over-the-counter, direct-to-consumer hearing devices. Specifically we were interested in assessing the benefits of these devices for middle-age people with no more than mild hearing loss. While some literature already exists on the effectiveness of devices of this type (Reed et al 2017, Cho et al 2019, Seol et al 2021, among others), these are primarily studies of individuals with greater degrees of hearing loss. Additionally, the goal of this study was to assess both the objective benefit of the devices, in terms of performance on a speech perception task, and to quantify subjective benefit in terms of self-rated listening effort while using the devices.

The study assesses four specific devices: Sound World Solutions CS50+, Nuheara IQ Buds, Tweak Focus, and Bose Hearphones. These four devices are all specifically classified as Personal Amplification Products, or PSAPs. Participants were randomly assigned to use one of these four devices during the study.

Study methods and procedures

The study consisted of three parts: intake procedures, where participants were given consent forms, performed cognitive and hearing assessments, and were fitted for the PSAP to which they were assigned; a speech perception task; and a brief post-test survey.

As part of the intake procedures, subjects completed the Montreal Cognitive Assessment (Nasreddine et al., 2005), after which audiometry and tympanometry were completed, and the subjects were fitted with a PSAP. Subjects were fitted binaurally, with suitable dome sizes and wire length selected to ensure an appropriate physical fit. Subjects assigned to the IQ Buds or CS50+ then performed an in-situ hearing test using the device's smartphone app. All devices were set to directional microphone mode (called 'focus', 'noisy', 'restaurant', and 'focused' for the IQ Buds, Tweak Focus, CS50+ and Hearphones, respectively) for the remainder of the time they were worn.

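### Does the SAP need a named primary test, a stated alpha and error control across its three repeated measures ANOVAs?

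*Combined protocol and SAP*

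**What the plan says.** Study objectives gives two aims. The first is "to assess both the objective benefit of the devices, in terms of performance on a speech perception task". The second is "to quantify subjective benefit in terms of self-rated listening effort while using the devices".

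The Statistical Analysis Plan section has one sentence of inferential method: "Statistical analysis will be done with separate Repeated Measures ANOVAs for Performance, Benefit, and Self-Rated Effort". The predictors are listed in two sentences. One begins "Between-subjects variables to be measured are device (i.e., which of the four devices the participant used), age, and hearing loss", and the other begins "Within-subject independent variables to be analyzed are device condition (i.e., with vs. without device) and acoustic properties of the stimuli" and goes on to target level, masker type and SNR. Benefit is derived from the Performance scores: "benefit will be measured as percent correct with device minus percent correct without device".

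The three outcomes are listed without rank. The plan states no alpha, sidedness, order of testing, adjustment or post hoc procedure, and no sample size or power. It calls the analyses neither confirmatory nor exploratory.

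**The concern.** The design has four devices, two device conditions, two levels, three maskers and two SNRs, so the ANOVAs produce many F tests. With no main test named, a reader might fear that any device-related term falling below 0.05 could become the headline for either goal. A planned result could then not be told from a chance one. The obvious remedy would be to state alpha, name a small confirmatory family, adjust within it (Holm, for example) and label the rest exploratory.

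**Working it through.** The plan gives no error rate to reproduce. Alpha = 0.05 is therefore an assumption, with 0.01 and 0.10 as the range, and the formula 1 − (1 − α)^k assumes that all nulls are true and the tests independent.

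**1. Counting device-related terms.** Write D for device, C for device condition, L for level, M for masker and S for SNR. Age and pure tone average are left out.

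- Performance, to two-way terms containing D or C: D, C, DC, DL, DM, DS, CL, CM, CS = 9.
- Benefit, to two-way terms: 4 main effects + 6 interactions = 10. Benefit is aided minus unaided Performance. Given matching models and complete data, its main effects therefore repeat DC, CL, CM and CS, which leaves 6 new tests.
- Effort is collected once per block ("At the end of each of the two blocks, subjects were asked to indicate how much effort they needed to expend"), so it has only D, C and DC = 3.
- Total: 9 + 6 + 3 = 18.
- Full factorials: Performance has 2^5 − 1 = 31 terms, of which 2^3 − 1 = 7 are purely acoustic. That gives 31 − 7 + 3 = 27, and Benefit adds none.

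**2. Which terms answer the goals.** Five of the 18 contain no C: D, DL, DM and DS on Performance, and D on Effort. They average over the unaided block and cannot show benefit. That leaves 13. Nine of these (CL, CM, CS and the six Benefit interactions) describe how benefit, or its difference between devices, varies with the acoustics or how acoustic factors combine. Four remain: C and DC, each for Performance and Effort.

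**3. Error rates.**

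| Tests read as headline | k | α = 0.05 | α = 0.01 | α = 0.10 |
|---|---|---|---|---|
| One per goal | 2 | 9.75% | 1.99% | 19% |
| C and DC for both outcomes | 4 | 18.5% | 3.9% | 34.4% |
| All terms with C, as counted above | 13 | 49% | 12% | – |
| All device-related, to two-way | 18 | 60% | 17% | – |
| All device-related, full factorial | 27 | 75% | 24% | – |

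For two correlated two-sided z tests at 0.05, simulation gives about 9.0% at correlation 0.5 and 7.8% at 0.8, so 9.75% is slightly high if speech scores and effort are positively related.

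**4. Cost of adjusting.** Holm over four tests starts at 0.05/4 = 0.0125. Take a test with an assumed 80% power at 5%; its standardised effect is 1.960 + 0.842 = 2.802. The critical value at 1.25% is 2.498, so power is Φ(2.802 − 2.498) = Φ(0.304) = 0.619. With F tests on 36 or 76 error degrees of freedom (assumed sample sizes of 40 and 80) it is 0.598 to 0.611. Over the whole Holm procedure, power per true effect is about 64%-65% if two of the four effects are real and 71%-73% if all four are. The loss is thus roughly 7 to 20 points.

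**5. What adjustment would leave open.** Four per-device benefit intervals at an ordinary 95% level carry 1 − 0.95^4 = 18.5% again if independent. Holm on the four tests does not cover these.

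**The case for a change.** The strongest case for a change is that the plan never calls itself exploratory, that Study objectives speaks of effectiveness, and that even the most favourable reading (one test per goal) gives nearly twice the nominal 5%. Wording costs nothing to add, and a reader of the eventual paper cannot recover the intended headline from this text.

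Part of that stands. The omission is real, and nothing blacked out or lost in conversion explains it. The Benefit ANOVA should not be counted as evidence separate from the Performance interactions it repeats. The between-device main effect on Performance is not a comparison of benefit.

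The rest does not carry a change. The 60% and 75% figures depend on treating as headlines terms that any sensible hierarchy would make exploratory. The documents do not settle which family is right: one test per goal, a fixed order, requiring both goals, or four tests with Holm are all defensible, and the second and third need no split of alpha. Whether to adjust at all across two separately stated goals is debatable.

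Timing also counts against the remedy. Study methods and procedures describes conduct and scoring as done ("Their responses were audio-recorded and analyzed and scored off-line"), while the analysis section is in the future tense. If results were already known when a hierarchy was set, naming confirmatory tests would not give error control.

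**Conclusion.** No change to the plan follows. The plan promises no familywise error rate, success rule or confirmatory claim, so its analysis contradicts none. Each F test, run as written under the usual ANOVA assumptions, is valid at its own level. What is missing is detail that analysts can fill sensibly when reporting: state the significance level used, lead with aided-minus-unaided estimates and confidence intervals for speech and effort, and treat the acoustic interactions as descriptive.

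The error rate that bears on the goals is about 9.75% (one test per goal) to 18.5% (four tests), under an assumed alpha of 0.05, true nulls and independence. It reaches 49%-75% only if far more terms are given equal weight. Formal control is a fair trade-off rather than a correction: it would cost roughly 7 to 20 points of power from an assumed 80%, for a family the documents do not define.
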